10.3.2.1 Reporting to the Competent Authority and Research Ethics Committee

Suspected Unexpected Serious Adverse Reactions

The Trials Office will report a minimal data set of all individual events categorised as a fatal or life threatening SUSAR to the Medicines and Healthcare products Regulatory Agency (MHRA and Research Ethics Committee (REC) within 7 days. Detailed follow-up information will be provided within an additional 8 days.

All other events categorised as SUSARs will be reported within 15 days.

Serious Adverse Reactions

The Trial Office will report details of all SARs (including SUSARs) to the MHRA and REC annually from the date of the Clinical Trial Authorisation, in the form of an Annual Safety Report.

Adverse Events

Details of all AEs will be reported to the MHRA on request.

Other Safety Issues Identified During the Course of the Trial

The MHRA and REC will be notified immediately if a significant safety issue is identified during the course of the trial.

10.3.2.2 Investigators

Details of all SUSARs and any other safety issue which arises during the course of the trial will be reported to Principal Investigators. A copy of any such correspondence should be filed in the ISF.

10.3.2.3 Data Monitoring Committee

The independent Data Monitoring Committee (DMC) will review all SAEs.

10.3.2.4 Manufacturer of Investigational Medicinal Product

All SAEs will be reported to the manufacturer of the IMP within 24 hours by fax.

STOMP Protocol

10.4 Deaths

All deaths that occur during the trial, or within 28 days after the administration of the last dose of trial medication, must be reported as follows:

Death clearly the result of disease progression should be documented on a Death Form but should not be reported as a SAE.

Where death is not due (or not clearly due) to progression of the disease under study, the AE causing the death must be reported as a SAE within **24h**. The report should contain a comment regarding the co-involvement of progression of disease, if appropriate, and should assign main and contributory causes of death. This information can be captured on the Death Form.

Deaths with an unknown cause should always be reported as a SAE. A post mortem maybe helpful in the assessment of the cause of death and, if performed, a copy of the post-mortem results should be forwarded to the STOMP Trial Office within the usual timeframes.

11.0 DATA HANDLING AND RECORD KEEPING

11.1 Data collection

The CRF must be completed, signed/dated and returned to the STOMP Trial Office by the Investigator or an authorised member of the site research team (as delegated on the Site Signature and Delegation Log) within the timeframe listed below in Table 11.1. The exception is the SAE Form which must be co-signed by the Investigator. See AE reporting Section 10.2 for further details.

Table 11.1 Standard forms and time points for data collection

Form Type	Time point
Eligibility Checklist	Complete during screening and return immediately following randomisation of the patient
Randomisation	Complete at randomisation and return immediately following randomisation of the patient
Baseline Form	Complete immediately following randomisation
Treatment Form	Complete 1 form per cycle of treatment (given for up to a maximum of 2 years). Complete the form at the end of the cycle and capture all information relevant to that cycle of treatment Please note: Chest x-rays are recorded on the odd numbered cycle forms and CT scans are recorded on the even numbered cycle forms
Response Form	Complete every 8 weeks until progression Please note: During treatment response data is recorded on even numbered cycle forms unless a scan is performed a cycle early due to disease progression
Adverse Event Monitoring Form	Complete at baseline (i.e. immediately following randomisation) and on completion of each treatment cycle (as per treatment forms)
Concomitant Medication Log	Complete at baseline (i.e. immediately following randomisation) and on completion of each treatment cycle (as per treatment forms)
Treatment Discontinuation Form	Complete when the patient finishes treatment regardless of cause

STOMP Protocol

Follow-up Form	Complete the first follow-up form 3 months after discontinuation of trial medication. Forms should then be returned every 3 months until death, withdrawal of consent for data transfer or the end of the trial.
SAE Form	Complete the form within 24h of first awareness of the event and fax to the Trials Office immediately (see Section 10.2)
Withdrawal Form	Complete when a patient withdraws from the trial
Death Form	Complete immediately on being notified of patient death
Pregnancy Notification Form	Complete immediately on being notified of patient pregnancy
Deviation Form	Completed immediately in the event of a deviation from the protocol
Patient Diaries	Completed by the patient during treatment and collected at each treatment visit
Quality of Life Questionnaire and (only for patients participating in the optional quality of life study)	Should be completed by the patient at baseline, on commencement of the start of each cycle of chemotherapy and treatment discontinuation
Quality of Life Compliance Form (only for patients participating in the optional quality of life study)	Complete when a patients quality of life assessment is due at baseline, on commencement of the start of each cycle of chemotherapy and at treatment discontinuation. Return attached to the Quality of Life Questionnaire

Entries on the CRF should be made in ballpoint pen, in black or blue ink, and must be legible. Any errors should be crossed out with a single stroke, the correction inserted and the change initialled and dated. If it is not obvious why a change has been made, an explanation should be written next to the change.

Data reported on each form should be consistent with the source data or the discrepancies should be explained. If information is not known, this must be clearly indicated on the form. All missing and ambiguous data will be queried. All sections of a form must be completed before returning to the STOMP Trial Office.

Source data consist of all the information in original records and certified copies of original records of clinical findings, observations, or other activities in the trial, which are necessary for the reconstruction and evaluation of the trial.

For the purposes of this trial the Quality of Life questionnaires and Patient Diaries will act as source data. The original documents will be sent to the STOMP Trial Office.

In all cases it remains the responsibility of the Investigator to ensure that the CRF has been completed correctly and that the data are accurate. The completed original CRF must be sent promptly to the STOMP Trial Office and a copy filed in the ISF.

Trial CRF may be amended by the Trial Office, as appropriate, throughout the duration of the trial. Whilst this will not constitute a protocol amendment, new versions of the CRF must be implemented by participating sites immediately on receipt.

12.0 ARCHIVING

It is the responsibility of the Principal Investigator to ensure all essential trial documentation and source records (e.g. signed Informed Consent Forms, ISF, Pharmacy Files, patients' hospital notes, copies of CRFs etc) at their site are securely retained for at least 15 years

STOMP Protocol

after the end of the trial. Participating centres will be sent a letter specifying the permissible disposal date.

13.0 QUALITY MANAGEMENT

The trial is being managed under the auspices of the CRCTU according to the current guidelines for GCP and according to their local procedures. Participating sites will be monitored by CRCTU staff to confirm compliance with the protocol, and the protection of patients' rights as detailed in the Declaration of Helsinki.

13.1 Site set up

All sites will be required to sign a Clinical Study Site Agreement prior to participation. In addition all participating Investigators will be asked to sign the necessary agreements, STOMP trial registration forms, and supply a current CV to the STOMP Trial Office. All members of the site research team will also be required to sign the Site Signature and Delegation Log, which should be returned to the Trial Office. Prior to commencing recruitment all sites will undergo a process of initiation. Key members of the site research team will be required to attend either a meeting or a teleconference covering aspects of the trial design, protocol procedures, AE reporting, collection and reporting of data and record keeping. Sites will be provided with an ISF and a Pharmacy File containing essential documentation, instructions, and other documentation required for the conduct of the trial. The Trial Office must be informed immediately of any change in the site research team.

13.2 On-site monitoring

Monitoring will be carried out as required following a risk assessment and as documented in the STOMP Quality Management Plan. Additional on-site monitoring visits may be triggered by poor CRF return, poor data quality, excess toxicity, excessive number of patient withdrawals or deviations. If a monitoring visit is required, the Trial Office will contact the site to arrange a date for the proposed visit and will provide the site with written confirmation. Investigators will allow the STOMP trial staff access to source documents as requested.

13.3 Central monitoring

Trials staff will be in regular contact with the site research team to check on progress and address any queries that they may have. Trials staff will check incoming CRF for compliance with the protocol, data consistency, missing data and timing. Where a patient has given explicit consent sites are also requested to send in copies of signed Informed Consent Forms for in-house review. Sites will be sent Data Clarification Forms requesting missing data or clarification of inconsistencies or discrepancies.

Sites may be suspended from further recruitment in the event of serious and persistent non-compliance with the protocol and/or GCP, and/or poor recruitment. Any major problems identified during monitoring may be reported to the Trial Management Group (TMG) and the relevant regulatory bodies. This includes reporting serious breaches of GCP and/or the trial protocol to the REC and the MHRA.

14.0 END OF TRIAL DEFINITION

For the purposes of Clinical Trial Authorisation (CTA) under the European Union Directive 2001/20/EC and REC approval, the trial is deemed to have ended 3 ½ years after the last patient has been enrolled into the trial. This will allow sufficient time for the completion of protocol procedures, data collection and data input. The STOMP Trial Office will notify the Sponsor, the MHRA and REC that the trial has ended and will provide them with a summary of the clinical trial report within 12 months of the end of trial.

15.0 STATISTICAL CONSIDERATIONS

15.1 Definition of primary outcome measure

The primary outcome measure is PFS time. PFS is defined as the interval in whole days between the date of randomisation into the trial and either the earliest date of detection of progression (where progression is defined by RECIST as an increase by 20% in the sum of tumour diameters or the appearance of new lesions) or date of death without recorded progression. For those patients who neither die nor experience progression during the course of the trial, progression-free survival time will be censored at the date when they were last known to be alive and free of progression.

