6.5 Follow up period

Patient follow-up will continue until 2 ½ years after the last patient has been recruited.

Patients who discontinue treatment for reasons other than progression should continue to have CT scans every 8 weeks until progression or alternatively until the follow-up period is complete.

The frequency of follow-up for patients, after the treatment phase has ended, will be at the discretion of the Investigator at the recruiting sites. It is anticipated that patients will be seen as a minimum every three months.

A Follow-up Form should be completed by the Investigator or a delegated member of the site research team and returned to the STOMP Trial Office every three months until the patient dies or the end of the follow-up period as defined above. This form will capture the date the patient was last seen in that 3 month follow-up period.

Every endeavour should be made to follow patients up in accordance with the protocol. Where patients fail to attend clinic the patient's GP should be contacted for follow-up information, patient consent permitting.

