7.4.2 Withdrawal from Treatment

If a patient chooses to withdraw from treatment only, the patient should discontinue treatment but continue to be assessed in accordance with the protocol (including continuation of CT scans).

If a patient wishes to withdraw from the trial (i.e. including trial specific assessments), but is willing for further data to be supplied to the STOMP Trial Office, then further routine “follow-up” data (e.g. progression status, survival, further treatment) will continue to be supplied by the Investigator to the STOMP Trial Office.

Patients may be discontinued from Investigational Medicinal Product (IMP) in the following situations:

- Patient decision. The patient is at any time free to discontinue trial drug, without prejudice to further treatment
- After suffering an AE
- Severe non-compliance to trial protocol
- Any CTCAE grade 3 or 4 events that have not reverted to CTCAE grade 1 or less within 4 weeks (28 days). At the Investigator’s discretion, following dose interruption, patients may be considered for dose reductions providing they have not already undergone the maximum number of dose reductions allowed - for guidelines see Section 6.2. However, if upon re-challenging with olaparib/placebo at the lowest reduced dose any CTCAE grade 3 or 4 AE recur, the patient must be discontinued
- Objective progression according to RECIST 1.1

If the patient decides to withdraw from the trial and is not willing to supply any further data then this wish should be explicitly stated in the source data.

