15.3 Trial design and sample size calculations

The power and sample size calculation is based on the primary outcome measure of PFS. A median PFS time of 4.8 months is assumed on the control arm. This has been calculated from the raw data of the relevant population from a recent large UK study in SCLC (Lee *et al* 2009). The STOMP trial population will be those patients in the Lee study that were categorised as responders after 4 cycles of chemotherapy. This trial aims to detect an improvement in median PFS to 7.8 months for either of the two experimental arms. A one-tailed significance level of 10% was selected, however, to adjust for multiplicity in comparing the two experimental arms separately to the control arm, the calculation is based on a log-rank test with a one-tailed significance level of 5% (equivalent to a two-tailed level of 10%).

The PFS analyses will be performed when approximately 105 events per comparison have occurred. With 105 events per comparison (assuming 1:1 randomisation) there is 80% power to detect a difference in treatments at a 5% 1-sided significance level, if the true (alternate) hazard ratio was hypothesised to be 0.62 (a reduction in risk of progression of 38%). If the median PFS in the control arm is expected to be 4.8 months, this equates to a 3 month increase in median PFS. Assuming 105 PFS events occur, an observed hazard ratio of 0.72 (a 28% reduction in risk of progression) will give a 1-sided p-value <0.05 within the

STOMP Protocol

trial (a hazard ratio of 0.72 corresponds to 1.9 month increase in median PFS, assuming exponential distribution and proportional hazards).

With the duration of the trial set as 2.5 years (24 months accrual and 6 months follow up) it is estimated that the trial will require 75 patients per treatment arm. Therefore in total a target recruitment of 225 patients is estimated to be required for this trial.

The sample size has been calculated employing the methodology for exponential survival using median survival times reported in Machin D, Campbell MJ, Tan SB, Tan SH: Sample Size Tables for Clinical Studies, 3rd Edition, 2009.

STOMP Protocol

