Incomplete Response/ Stable Disease (SD)	Persistence of one or more non-target lesion(s)
Progressive Disease (PD)	Appearance of one or more new lesions and/or unequivocal progression of existing non-target lesions ¹

Notes:

1. To achieve “unequivocal progression” on the basis of the non-target disease, there must be an overall level of substantial worsening in non-target disease such that, even in presence of SD or PR in target disease, the overall tumour burden has increased sufficiently to merit discontinuation of therapy.

STOMP Protocol

C. Overall Responses for all Possible Combinations of Tumour Responses in Target and Non-target Lesions With or Without the Appearance of New Lesions

Target Lesions	Non-target Lesions	New Lesions	Overall Response
None	None	No	Non - PD
Complete response (CR)	CR	No	CR
Complete response (CR)	Non-CR/non-PD	No	PR
Complete response (CR)	Not evaluated	No	PR
Partial response (PR)	Non-PD	No	PR
Stable disease (SD)	Non-PD	No	SD
Not all evaluated	Non-PD	No	Not evaluable (NE)
Progressive disease (PD)	Any	Yes or no	PD
Any	PD	Yes or no	PD
Any	Any	Yes	PD

Frequency of Tumour Re-evaluations

For the STOMP trial, PFS will be evaluated radiologically by a CT scan at baseline and at 8 weekly intervals until progression.

For patients who discontinue treatment prior to progression CT scans should continue to be performed in accordance with the Scheme of Trial Assessments (Table 7.1).

STOMP Protocol

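### The PFS censoring date in section 15.1 is not tied to a CT, so a patient who leaves the scans but stays in routine follow-up can be credited with progression-free time that no scan has verified

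*Protocol*

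**What the plan says.** Section 15.1 of the protocol makes the PFS event RECIST progression or "date of death without recorded progression". For everyone else, "progression-free survival time will be censored at the date when they were last known to be alive and free of progression".

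Progression is looked for by CT. Section 7.3 sets tumour assessments every 8 weeks, and Appendix 3 states that "PFS will be evaluated radiologically by a CT scan at baseline and at 8 weekly intervals until progression".

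Three other sections decide what happens to a patient who is no longer scanned:

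- Section 7.4.2 separates stopping the drug, after which CTs continue, from leaving trial-specific assessments while still allowing data to be passed on. Of those routine data it says: "e.g. progression status, survival, further treatment) will continue to be supplied by the Investigator".
- Section 6.5 has a Follow-up Form returned every three months: "This form will capture the date the patient was last seen in that 3 month follow-up period". No scan is required for it.
- Section 7.2 asks for a CT to confirm progression suspected clinically or on chest X-ray. Nothing asks for a CT before a patient is recorded as progression-free.

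Section 15.4 says only that an interval-censored analysis of PFS will be considered.

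**The concern.** Events and censoring times come from different sources. An event is normally dated by a scan on an 8-week grid. A censoring time may be dated by a clinic visit or a telephone report.

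Take a patient who leaves the scans after the month-2 CT and is reported well in clinic at month 8. Read literally, section 15.1 censors at month 8. Six of those eight months (8 − 2) are counted as progression-free although the method that detects progression in other patients was not applied.

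If such patients are equally common in both arms of a comparison, the effect largely cancels in the hazard ratio. If not, the arm with more of them looks better. At stake are the primary hazard ratio, its one-sided test, and the 4-month progression-free rate, which is a secondary outcome.

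**Working it through.** **1. The plan's own figure.** For 105 events per comparison, section 15.3 claims 80% power at a one-sided 5% level, taking 0.62 as the hazard ratio under the alternative. With medians of 4.8 and 7.8 months the ratio is 4.8/7.8 = 0.615. Schoenfeld's formula at 1:1 allocation gives d = 4(1.645 + 0.842)²/(ln 0.615)² = 24.73/0.2357 = 105 events, as stated. The rounded ratio 0.62 gives 109, and 78.9% power at 105. The standard error of the log hazard ratio at 105 events is 2/√105 = 0.195, so the critical hazard ratio is exp(−1.645 × 0.195) = 0.725 (protocol: 0.72). The censoring rule does not enter this calculation.

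**2. Who is affected.**

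| Patient | Under 15.1 as written |
|---|---|
| Stops drug, keeps scanning | Not affected |
| Leaves scans, dies without recorded progression | Event at death; the censoring sentence does not apply |
| Leaves scans, progression later reported | Event, possibly late; the censoring sentence does not apply |
| Leaves scans, no event recorded | Censored at the latest favourable report, with no scan behind it |

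Only the last row is governed by the sentence in question.

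**3. Size with no drug effect.** The protocol gives no off-scan rates, so these are assumptions. Common settings: 75 against 75 patients, exponential PFS with control median 4.8 months, CT every 8 weeks, 24 months' accrual plus 6 months' follow-up.

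*Set A*: patients leave at months 1–4, only death is caught afterwards, median survival after progression is 4 months; 3,000 trials per row.

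| Leaving, arm 1 / arm 2 | As written: HR, one-sided error | Last-CT censoring: HR, error |
|---|---|---|
| 10% / 3% | 0.97, 7.5% | 1.00, 5.5% |
| 15% / 3% | 0.94, 9.2% | 0.99, 5.6% |
| 20% / 5% | 0.93, 10.7% | 1.00, 6.2% |
| 10% / 10% | no bias | no bias |

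*Set B*: patients leave at months 0–6, and the later event is recorded a median of 3 or 6 months after true progression (two values per cell, in that order); 2,000 trials each.

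| Leaving, arm 1 / arm 2 | As written: HR, one-sided error | Last-CT censoring: HR, error |
|---|---|---|
| 10% / 10% | 1.01, 1.00; 4.5%, 5.7% | 1.01, 1.00; 4.0%, 5.2% |
| 10% / 5% | 0.99, 0.97; 6.2%, 6.9% | 1.00, 1.00; 4.4%, 5.2% |
| 20% / 10% | 0.97, 0.94; 6.8%, 9.2% | 1.01, 1.00; 4.4%, 5.2% |
| 20% / 5% | 0.95, 0.91; 10.0%, 12.7% | 1.00, 0.99; 6.0%, 5.0% |
| 10% / 20% | 1.03, 1.06; 3.4%, 2.2% | 1.00, 1.00; 4.9%, 4.6% |

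Monte Carlo error on a 5% rate with 2,000 trials is √(0.05 × 0.95/2000) = 0.5 points. The simulated trials run to month 30 and carry about 128 events, not 105.

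**4. Check of scale at 105 events.** A null hazard ratio of 0.97 shifts the statistic by 0.030/0.195 = 0.16 SE, giving an error of Φ(−1.645 + 0.16) = 6.8%. A ratio of 0.94 shifts it by 0.062/0.195 = 0.32 SE, giving 9.2%. These agree with the simulated values.

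**5. What last-CT censoring does not cure.**

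- When half of off-scan progressions are still reported clinically, the hazard ratio as written is only about 0.98, and last-CT censoring gives 1.01–1.03.
- At a true ratio of 0.615 with 20% / 5% leaving, set B gives 0.57–0.59 as written, 0.62–0.64 with last-CT censoring, and 0.61 with complete scanning.
- With 10–15% against 3% leaving and only death detected, the 4-month rate in the arm with more leavers is inflated by 1.7–2.5 points as written and by about 0.8–1.4 points after last-CT censoring alone.

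**The case against.** **The wording may already mean the last CT.** Section 15.2 censors overall survival when the patient was last known to be alive; 15.1 adds freedom from progression, and Appendix 3 says PFS is evaluated radiologically. No section says that the Follow-up Form date sets PFS censoring. This stands in part: the text is loose and does not reject the last-CT date. But 15.1 fixes a date rather than leaving it open, and two analysts could choose different ones. The SAP is not at hand and may settle it.

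**The route is narrow.** Sections 6.5, 7.1.6 and 7.4.2 tell patients who only stop the drug to keep scanning, so a separate withdrawal from trial assessments is needed. Progression status is still supplied afterwards, and section 7.2 asks for a CT if progression is suspected. This stands, and it makes the death-only scenario close to a worst case.

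**A reader might infer that the rule favours olaparib**, on the reasoning that toxicity leads to stopping and stopping leads to leaving the scans. The documents do not support this. They give no off-scan rate by arm, the trial is double-blind, section 1.4 describes olaparib monotherapy as generally well tolerated, and stopping the drug does not end the scans. The 2:1 allocation overall would put more such patients on olaparib by count, but equal rates give no material bias. More leaving on placebo would bias against olaparib (1.03–1.06 in the last row of set B).

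**A reader might also blame the censoring sentence for late deaths**, such as an unscanned patient dying at month 11. That death is an event at month 11 under 15.1 and would remain so after the sentence is changed.

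**The effect is small.** A null ratio of 0.94–0.97 is 0.2–0.3 SE, far from the critical 0.72. True for the estimate, but in these scenarios the error rate still rises by half or more above its nominal 5%.

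**Conclusion.** The point holds as a conditional weakness in the primary endpoint definition. Section 15.1 lets progression-free time accrue without a scan, while sections 7.3 and Appendix 3 base PFS on 8-weekly CT, and sections 7.4.2 and 6.5 supply the route.

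The direction is unknown and the size modest. With 10–20% leaving on one arm, 3–5% on the other and little off-scan progression detected, the null hazard ratio is about 0.93–0.98 with one-sided error about 7–11%. The most extreme setting tried reached 0.91 and about 13%. The bias is smaller if progression is still reported clinically, and about nil at equal rates. Off-scan shares, leaving times, and survival or reporting delay after progression are all assumptions. The 105-event target is unaffected.

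The change is worth making because it is cheap and guards the primary comparison against bias in either direction. It does not show that the planned result would be wrong.

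**What to change.** 1. In section 15.1, censor patients with neither progression nor death at the date of their last RECIST-evaluable CT, or at randomisation if there is none after baseline. Keep later contact dates for overall survival only.
2. Prespecify one sensitivity analysis in which any progression or death first recorded after two or more missed 8-weekly scans is censored at the last CT. This, not the new sentence, deals with late deaths and late clinical reports.
3. Report by arm how many patients left the scans before progression, and when. That shows whether the conditional bias applies.

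The cost is one sentence, one extra analysis and one table. CT results are already collected on the even-numbered Treatment Forms and the Response Form (Table 11.1). The downside is slightly shorter follow-up for censored patients and a few fewer events in the sensitivity analysis. Because last-CT censoring can lean slightly the other way when off-scan progression is well reported (1.01–1.03 above), the two analyses should be read together.
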